The findings of this study will inform clinicians and investigators whether use of mobile seat interface pressure mapping as a compensatory-based intervention has a positive impact on trunk movement and self-efficacy for completing weight shifts in wheelchair users who lack sensation. Another contribution of this work is an exploration of the relationship between self-efficacy and movement in wheelchair users.

Primary Aim. Trunk movement in seated wheelchair users with SCI will increase when the user has access to a mobile seat interface pressure mapping system to self-monitor pressure distribution on their wheelchair seat cushion.

Secondary Aim. Self-efficacy for use of weight shifts as a pressure ulcer prevention strategy in wheelchair users with SCI will increase through structured education and with access to the mobile seat interface pressure mapping system to self-monitor pressure distribution on their wheelchair seat cushion.

Hypotheses:

Hypothesis 1. Weight shifts (counts of forward and side leans) will be higher with access to the mobile seat interface pressure mapping system than without it.

Hypothesis 2. Overall trunk movement (counts of vector magnitude) will be higher with access to the mobile seat interface pressure mapping system than without it.

Hypothesis 3. Self-efficacy rating immediately after education for weight shifts will be higher than self-efficacy rating taken prior to education.

Hypothesis 4. Self-efficacy rating during access to mobile seat interface pressure mapping at home will be higher than rating after education for weight shifts and higher than rating during phases when there is no access to the pressure mapping system.

Background (Include relevant experience, gaps in current knowledge, preliminary data, etc.):

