This research study addresses pressure ulcer prevention through introduction of a novel compensatory approach to improve weight shifting movements and self-efficacy in achieving the goal of preventing pressure ulcers. It is proposed that use of an on-demand, real-time, visual display of seat interface pressure ([name], 2013; [name], Rindflesch, & [name], 2013) will provide key feedback that allows wheelchair users with poor or absent sensation to immediately see the results of weight shifting and thus feel more confident in their ability to manage the build-up of pressure by using weight shifts effectively. Use of seat interface pressure mapping throughout one's typical daily routine has the potential to impact self-efficacy for managing skin health and also to improve weight shift adherence over time. This purpose of this study is to explore the potential benefit

of seat interface pressure mapping as a compensatory intervention strategy for impaired sensation in spinal cord injured wheelchair users.

Study Design and Methods

Methods: *Describe, in detail, the research activities that will be conducted under this protocol:*

This is a longitudinal, within-subject, repeated (A-B-A-B) measures design. Two interventions will be provided: structured education regarding pressure ulcer prevention through weight shifts at start of study and use of a mobile seat interface pressure map (IPM). Outcome measures include self-efficacy (SE) for weight shift movements and a measure for trunk movements. Figure 1 provides an overview of the design and sequence of measurements.

[figure not shown]

Figure 1. Details of study design.

Independent variables (IV). There are two independent variables in this study.

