- 1. Access to the mobile seat interface pressure mapping system (IPM) as a visual feedback system.** This mobile IPM system was designed to provide visual information about seat interface pressure distribution to compensate for lack of sensation on the sitting surface. This variable will be toggled on and off between the A and B phases of the study. The participants will have access to the visual feedback while learning how to complete weight shift maneuvers at the initial visit and then again at home during the A phases (weeks 2 and 4). During the B phases (weeks 1 and 3), they will not have access to the visual feedback from the pressure map. The pressure mapping system consists of a commercially available pressure mat by Vista Medical, and a mobile web-application developed by the research team through a CoDE award provided by the Center for Innovation in 2012 to display the pressure map information on a smartphone screen. The pressure mat connects to the smartphone via Wifi. The smartphone accesses the web application via the phone's data plan while connected to

the mat to display the pressure readings to the user on the phone. No information about the individual, except for the research participant ID number is transmitted to the web application. Each research participant will have a unique password associated with their own ID to use when they log into the web application. The web application resides on a Mayo Clinic server.

2. Education about pressure ulcer risk and how to perform weight shift movements.

Structured education for performance weight shift maneuvers and pressure ulcer prevention will occur during the initial visit. The education method used aligns with principles of the social cognitive theory to facilitate learning. The purpose in providing the education is to ensure all of the participants receive uniform instruction in how to perform weight shifts and to facilitate understanding of the importance of completing them as a protective measure against pressure ulcer development. Because each participant will come into the study at varying levels of understanding about pressure ulcer risk and knowledge of how to complete weight shift maneuvers, the education component is critical to ensure all participants are provided with the same information in the same way.

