Dependent variables. There are two dependent variables in this study: overall trunk movement (vector magnitude and weight shift count) measured through a single tri-axial accelerometer and self-efficacy for performing weight shifts to prevent pressure ulcers measured with four items on a self-efficacy assessment written specifically for this study.

1. Trunk movement. Trunk movement will be measured using a single tri-axial accelerometer attached to the participant's sternum with a chest strap. The accelerometer used in this study is the Actigraph GT3X+ (Culiolo & Shaw, 2016). The GT3X+ measures accelerations within a dynamic range of +/- 6 units of gravity (G) in three planes of trunk motion, the vertical, anteroposterior, and mediolateral. The accelerometer will be worn throughout the study while the individual is in their wheelchair and taken off at night when sleeping. Trunk movement will be reported in two ways: vector magnitude for counting total movements of the trunk and counts of specific weight shift movement magnitudes based on offset angles of the accelerometer measures. Frequency of data collection will be 30Hz. When measuring continuously for 24 hours/day at 30Hz, the published battery life is 22.5 days and memory limit is 42.5 days. This will require that the participants charge the battery midway through the study. A more detailed description of the specific variables follows.

a. Vector magnitude. A total count of trunk movements in the form of vector magnitude will be averaged across each phase for each participant. The Actigraph GT3X+ provides raw values in each of the three axes. A composite vector magnitude of these three axes (VM) in a specific period of time is a "count" of movement. VM is the square root of the sum of each axis squared. VM will be calculated per second of wear time. For each of the 7 days in a phase, there will be a total VM, which will be graphically portrayed by day for visual analysis of trends for movement within each phase. The overall VM for each phase will be the average VM across the 7 days. This average VM per phase (A1, B1, A2, B2) will be used as the dependent variable for overall trunk movement.

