2. **Self-efficacy for performing weight shifts.** The second dependent variable, self-efficacy, is measured with a series of four individual questions about self-efficacy for weight shifts for pressure ulcer prevention (Appendix A). Each question is answered by choosing a number from 0-100 to indicate confidence level. This assessment includes an initial question that targets an individual's outcome belief about whether they believe that completing weight shifts will prevent pressure ulcers. This is followed by three questions about their own judgement of their immediate capability to complete weight shift maneuvers based on three criteria: effectiveness (moving enough to impact pressure distribution), consistency (completing weight shifts every half hour), and duration (holding weight shifts for two minutes). The items were written following principles outlined in Albert Bandura's guide to developing self-efficacy assessments (A. Bandura, 2006).

The score for each of the four items will allow preliminary analysis of any change in self-efficacy for specific components of performing weight shifts with the outcome of pressure ulcer prevention. The self-efficacy questions (SE) will be administered in person or by phone a total of 7 times: at start of initial session before any education, at end of session when education is completed, on day 2 when participant has been home for 1 day but no other intervention has been provided (test-retest), and at the end of each of the four phases. The self-efficacy survey will be given twice during the initial visit, 4 times over the phone when participant is called each week, and 1 time during the last visit for a total of 7 times.

Additional demographic information will be obtained from existing medical records and will include date of onset of spinal cord injury, date of birth, history of pressure ulcers on sitting surface, history of pressure ulcer repair surgery, level of spinal cord injury and severity of injury.

Resources: *Describe the available resources to conduct the research (personnel, time, facilities, mentor commitment, etc.):*

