Subject ID, subject code or any other person-specific unique identifying number, characteristic or code that can link the subject to their medical data	X	
Dates: All elements of dates [month, day, and year] directly related to an individual, their birth date, date of death, date of diagnosis, etc. Note: Recording a year only is not a unique identifier.	X	
Social Security number		
Medical device identifiers and serial numbers		
Biometric identifiers, including finger and voice prints, full face photographic images and any comparable images		
Web Universal Resource Locators (URLs), Internet Protocol (IP) address numbers, email address		
Street address, city, county, precinct, zip code, and their equivalent geocodes		
Phone or fax numbers	X	
Account, member, certificate or professional license numbers, health beneficiary numbers		
Vehicle identifiers and serial numbers, including license plate numbers		

Check 'None' when none of the identifiers listed above will be recorded, maintained, or shared during the conduct of this study. (exempt category 4)	 None	 None
---	-------------------------------	--

Data Analysis

Power analyses and study endpoints are not required for minimal risk research, pilot or feasibility studies.

No statistical information. *If checked, please explain:*

Data Analysis Plan:

Post-processing of the Actigraph data will be completed with custom software in MATLAB (Mathworks, Natick, MA).

The **vector magnitude** for each second of data during wear-times will be classified as a period of activity or inactivity. Additionally, total vector magnitude of movement for each day will be determined by summing the VM of all active wear-times. Then, for each 7-day phase, the daily values will be averaged for a resulting average phase VM. There will be an average phase VM for each phase A1, B1, A2, and B2.

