Weight shifts will be counted as described earlier based on offset angles. The average number of weight shifts for each type of weight shift will be documented by phases A1, B2, A2, B2. The analyses to test the primary hypothesis that overall trunk movement (vector magnitude) and weight shifts will increase in frequency with the use of the mobile pressuring mapping system will be tested using Linear Mixed Effects Regression. When appropriate, post-hoc tests will be performed to test main effects. If a phase x session interaction is present, post hoc tests to analyze and interpret the interaction will be used. Significance is set at $\alpha=0.05$.

Self-efficacy scores will be analyzed by comparing scores SE #1 vs #2, #2 vs #3 (test-retest), and #4 vs #5 vs #6 vs #7 to determine effect of education and use of mobile IPM on self-efficacy. The analyses to test the secondary hypothesis that the scores for the self-efficacy items will increase after education and will increase again with the use of the mobile pressuring mapping system will be tested using Linear Mixed Effects Regression. When appropriate, post-hoc tests will be performed to test main effects. If a phase x session interaction is present, post hoc tests to analyze and interpret the interaction will be used. Significance is set at $\alpha=0.05$.

The results will help determine if there is a cause/effect relationship between use of the pressure map and any increase in weight shifts if that is detected and if results are significant, we can conclude that use of the map resulted in increased movement. We can't conclude that there will be a reduction in

pressure ulcers but we can say that weight shifts, a factor known to contribute to reduced pressure ulcer risk, increases when a wheelchair user has access to a compensatory assistive device to accommodate reduced sensation. The same is true for results of the self-efficacy assessments. We would expect the mean score to improve at each subsequent time-point.

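### The listed self-efficacy comparisons never test map ratings against the post-education rating (first half of Hypothesis 4), and the four-way phase comparison does not by itself isolate map from no-map

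*Combined protocol and SAP*

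**What the plan says.** Hypothesis 4 (Hypotheses) states that the self-efficacy rating during map access "at home will be higher than rating after education for weight shifts and higher than rating during phases when there is no access" to the system. It makes two claims: above the post-education level, and above the no-map phases.

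The self-efficacy paragraph of the Data Analysis Plan specifies "comparing scores SE #1 vs #2, #2 vs #3 (test-retest), and #4 vs #5 vs #6 vs #7". It then says that a rise after education and a further rise with the map will be tested by linear mixed effects regression at a significance level of 0.05. Post-hoc tests follow where appropriate or if phase and session interact.

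Dependent variables, item 2, gives the timing: before education, after education, day 2, "and at the end of each of the four phases". In that order #1 is pre-education, #2 post-education, #3 the retest, and #4 to #7 the ends of weeks 1 to 4.

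Independent variables, item 1, places the map "again at home during the A phases (weeks 2 and 4). During the B phases (weeks 1 and 3), they will not have access". Elsewhere the design is a "repeated (A-B-A-B) measures design", and the phases run A1, B1, A2, B2 ("This average VM per phase (A1, B1, A2, B2) will be used as the dependent variable for overall trunk movement"; "There will be an average phase VM for each phase A1, B1, A2, and B2").

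The final paragraph extends its causal reading of the movement results to self-efficacy and expects the mean score to rise from each time-point to the next.

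**The concern.** A reader who follows the listed comparisons would finish without testing the first half of Hypothesis 4. The sentence about a further rise with the map shows the intent but names no reference rating. It could be #2, #3 or the no-map phases, and these are different claims. The choice would be made at analysis.

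For the second half, a significant four-way result says only that the four phase-end means are not all equal. The plan intends to read self-efficacy results causally, so a steady rise through familiarity or repeated questioning could be credited to the map.

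The A/B labels add a practical risk. Taken as a time order, A-B-A-B puts A first, whereas the stated weeks put A second and fourth. An analyst who codes by label would reverse the sign of the map contrast.

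**Working it through.** **Inputs.** Seven ratings (2 at the first visit + 4 by phone + 1 at the last visit = 7; by time-point 1 + 1 + 1 + 4 = 7). Target accrual is 30. Map weeks are 2 and 4 as stated, so #5 and #7 are map ratings and #4 and #6 no-map ratings. The documents give no SD, effect size, drift or power figure, so there is none to reproduce. Every effect below is an assumption in residual SD units, with independent residuals around a participant effect, no dropout and two-sided alpha 0.05.

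**Is half (i) reachable from the list?** The list forms two separate blocks, {#1, #2, #3} and {#4, #5, #6, #7}. Any contrast built from it has weights summing to zero within each block. The contrast needed is (a) = mean(#5,#7) − #2, whose weights sum to −1 in the first block and +1 in the second. It cannot be built. In rank terms, the list has rank 2 + 3 = 5, and adding (a) raises it to 6. The same holds for mean(#4,#6) − #2, so the gap does not depend on the phase order.

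**Is half (ii) reachable?** The contrast (b) = mean(#5,#7) − mean(#4,#6) lies inside the second block (rank stays 5). It is available, but the four-way test spreads over 3 degrees of freedom, not this one.

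**Power and rejection.** The noncentrality is λ = 30 × (contrast)² / Σw² for a single contrast and 30 × Σ(μ − mean)² for the four-way test. For (b), Σw² = 4 × 0.25 = 1. Error df are 87 = 3 × 29 when #4 to #7 are fitted alone.

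- Full reversal, means (0, 0.5, 0, 0.5): (b) λ = 30 × 0.25 = 7.5, power 77%. Four-way λ = 30 × 4 × 0.0625 = 7.5 on 3 df, power 60%.
- Gain persists, means (0, 0.5, 0.5, 0.5): (b) estimates 0.25, λ = 30 × 0.0625 = 1.875, power 27%. Four-way λ = 30 × 0.1875 = 5.625, power 47%.
- Drift of 0.2 per week and no map effect, means (0, 0.2, 0.4, 0.6): four-way λ = 30 × 0.2 = 6, rejects 50%. (b) estimates 0.2, λ = 1.2, rejects 19%.
- Same drift, contrast (a): #5 and #7 average (2 + 4)/2 = 3 weeks after #2, so it estimates 3 × 0.2 = 0.6. With Σw² = 1 + 0.25 + 0.25 = 1.5, λ = 30 × 0.36/1.5 = 7.2 on 1 and 174 df, rejects 76%.

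At drifts of 0.1 and 0.3 per week the four-way test rejects 15% and 87%, (b) 8% and 37%, and (a) 27% and 98%. In a seven-level model all error df become 6 × 29 = 174, which moves the (b) and four-way figures by about one percentage point at most.

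**Removing linear time.** Weights (−1/4, 3/4, −3/4, 1/4) on #4 to #7 give a weekly trend of −0.25 + 1.5 − 2.25 + 1 = 0. Their Σw² = 20/16 = 1.25, so the variance is 1.25 times that of (b). With drift alone this version rejects 5%. Its power at 0.5 SD is 68% under full reversal and 9% if the gain persists.

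**If the other phase order were confirmed.** Swapping positions would give (3/4, −1/4, 1/4, −3/4), whose trend is 0.75 − 0.5 + 0.75 − 3 = −2 per unit of weekly drift. Reversing signs, (1/4, −3/4, 3/4, −1/4), keeps it at 0.

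**The case against.** The plan has more than the list. The mixed-model sentence commits to testing a further rise with the map, and the post-education level is its most natural reference. Post-hoc tests are provided for. If phase is coded map/no-map and session as first/second cycle, the phase main effect is contrast (b). Under Weight shift count the plan says that phase averages can be compared between control and intervention conditions, which suggests that coding. An overall test followed by post-hoc tests is ordinary practice, and by the figures above it does better than (b) if the gain persists. Self-efficacy is also a secondary aim.

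This softens the second half considerably. It does not repair the first: the reference rating is unnamed, #2 belongs to no phase or cycle, and a phase-by-session model cannot produce (a). For the second half, the shown text defines neither factor. The methods say "Figure 1 provides an overview of the design and sequence of measurements", and that figure is not available here, so it may settle the coding.

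Three stronger readings are tempting and not supported. First, a reader might infer that Hypothesis 4 was dropped; the stated intent to test a further rise shows otherwise. Second, a reader might infer that the map weeks are unknown. The weeks are given explicitly, and the statement that no other intervention has been provided by day 2 agrees with a first week without the map. What conflicts is the lettering. Third, a reader might infer that a steady rise contradicts Hypothesis 4. Read as averages, it does not: with the map in weeks 2 and 4, a steady rise makes (b) positive. Hypothesis 4 does not say that ratings fall on withdrawal.

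**Conclusion.** The concern holds. The first half of Hypothesis 4 is not tested by any listed comparison, and this follows from the text without any assumed effect. The second half is a matter of definition: the contrast is within reach, but the plan does not say that it is the test. The plan's expected steady rise would make both (a) and (b) positive with no map effect, which matters because a causal reading is planned.

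The size is illustrative: at 0.5 SD with full reversal, 77% power for (b) against 60% for the four-way test; if the gain persists, 27% against 47%; under a 0.2 SD weekly drift alone, the four-way test rejects 50%. These figures rest on 30 complete participants and assumed effects. It should be fixed, as a gap in a secondary aim that wording can close.

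**What to change.** 1. Reconcile the A/B labels in the design description, the vector magnitude section and the Data Analysis Plan with the weeks under Independent variables, and state which rating numbers are map ratings.
2. For each item, fit a mixed model with a random participant effect and time as a seven-level factor (#1 to #7), so that #2 and the phase-end ratings sit in one model.
3. Pre-specify (a) mean(#5,#7) − #2, reported as a comparison of levels that a time trend alone can produce, and (b) mean(#5,#7) − mean(#4,#6) as the test of the second half. Keep the four-way result as description.
4. As a sensitivity analysis, report the map effect adjusted for linear time with weights (−1/4, 3/4, −3/4, 1/4) on #4 to #7. If the opposite order is confirmed, exchange the map and no-map ratings in (a) and (b), but reverse the signs of these weights; do not swap their positions.
5. Replace the closing expectation of a rise at every time-point with Hypothesis 4's own prediction: map ratings above #2 and above no-map ratings. Do not add a predicted fall on withdrawal.

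**Cost.** Analysis wording only; all seven ratings are already planned. Contrast (b) still carries one week of drift and loses power if the gain persists. The trend-adjusted version has 1.25 times the variance and recovers only a quarter of a persisting gain. Contrast (a) adds one test for each of the four items.

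### The before-after self-efficacy contrast at the first visit (SE #1 vs #2) cannot identify an effect of education: it has no comparator, and the pressure map is shown during the same session

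*Combined protocol and SAP*

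**What the plan says.** **Design.** Study Design and Methods states: "This is a longitudinal, within-subject, repeated (A-B-A-B) measures design". Two independent variables are declared, map access and education. Only map access is alternated between phases.

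**Education.** Under Independent variables, item 2: "Structured education for performance weight shift maneuvers and pressure ulcer prevention will occur during the initial visit". Its stated reason is to "ensure all participants are provided with the same information in the same way". Nobody has education withheld, delayed or withdrawn.

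**The map in the session.** Item 1 of the same section gives participants the visual feedback while they learn the manoeuvres at the initial visit. The aims section likewise treats the map as part of the education.

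**Ratings.** Under Dependent variables, item 2, four items are each scored 0-100 on seven occasions. The first two are taken "at start of initial session before any education, at end of session when education is completed". The third is on day 2, at home, labelled test-retest. The last four are at the ends of the four phases.

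**Hypothesis 3.** "Self-efficacy rating immediately after education for weight shifts will be higher than self-efficacy rating taken prior to education".

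**Analysis.** The Data Analysis Plan lists #1 vs #2, #2 vs #3, and #4 vs #5 vs #6 vs #7, and gives their purpose as "to determine effect of education and use of mobile IPM on self-efficacy". The closing paragraph discusses cause and effect for map use and weight shifts, then adds: "The same is true for results of the self-efficacy assessments".

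**The concern.** The stated purpose gives #1 vs #2 a causal job. A single-group before-after difference within one visit cannot do it. The reversal design helps with the map, because the map is removed and returned. It gives no such help with education, which happens once and stays in place.

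At least three other things change between the two ratings or act on the second:

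- participants see their own pressure map;
- they answer the same four study-specific items again within one visit;
- they do so in person, at the end of a session that has just taught them weight shifts and why these matter.

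Nothing in the plan estimates or removes any of these. Hypothesis 3 and part of the Secondary Aim rest on this contrast, so a significant result could be published as an education effect that the trial cannot identify.

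**Working it through.** The plan gives no power, effect size or SD for self-efficacy, so it has no figure of its own to reproduce.

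**Step 1: does any planned contrast isolate education?**

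| Contrast | What differs between the ratings | Education isolated? |
|---|---|---|
| #1 vs #2 | education, map viewing, repeat asking, demand | No |
| #2 vs #3 | one day at home; both ratings follow education | No |
| #4 to #7 | map access on or off, and time; all follow education | No |

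No contrast compares education with its absence while holding the rest fixed. This does not depend on any number.

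**Step 2: how large must a shift be to reach significance?**

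Inputs:

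- n = 30 (target accrual) and alpha = 0.05 (Data Analysis Plan).
- Two-sided testing is assumed, because sidedness is not stated.
- The SD of the within-person change is not given; 10 to 25 points is assumed.

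With two time points, complete data and a random intercept, the planned mixed model is equivalent to a paired t-test. The change is significant when

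|mean change| / SD ≥ t(0.975; n−1) / √n

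For n = 30 this is 2.045 / 5.477 = 0.373. With fewer completers it is 0.396 (n = 27) or 0.422 (n = 24).

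**Step 3: how often would a shift not due to education be significant?**

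The probability is P(|T| > 2.045), where T is noncentral t with 29 df and noncentrality (shift / SD) × √30. For example, 5 points with SD 15 gives (5/15) × 5.477 = 1.826, and a probability of 0.423.

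| Assumed SD of change | Smallest significant mean shift | 2-point shift | 5-point shift | 10-point shift |
|---|---|---|---|---|
| 10 | 3.7 points | 19% | 75% | >99% |
| 15 | 5.6 points | 11% | 42% | 94% |
| 20 | 7.5 points | 8% | 26% | 75% |
| 25 | 9.3 points | 7% | 19% | 56% |

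These are per item, with no true education effect. Four items are scored separately and no multiplicity adjustment is stated, so the chance that at least one is significant is higher.

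**Step 4: what does the day-2 rating add?**

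The protocol gives two ratings at the initial visit, four by phone and one at the last visit (2 + 4 + 1 = 7). Ratings #1 and #2 are therefore in person, #3 to #6 by phone, and #7 in person. Rating #3 shows whether a rise lasts a day at home. It also follows education, so it cannot estimate re-asking or drift before education. The contrast #1 vs #3 is not listed.

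**The case against.** **Hypothesis 3 is temporal.** It predicts a higher rating straight after education than before it, and #1 vs #2 tests exactly that. Three of the four items ask about immediate capability, so a quick rise in stated confidence is arguably what they are meant to measure. This stands: the test is legitimate. The problem is attributing the change to education.

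**The closing paragraph names only the map.** A reader might infer that the plan expressly claims cause and effect for education. The documents do not clearly support that. The explicit causal sentences concern map use and weight shifts, and it is ambiguous how far "The same is true for results of the self-efficacy assessments" reaches. The point rests instead on the explicit purpose statement, "to determine effect of education and use of mobile IPM on self-efficacy".

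**The size of any response shift is unknown.** A reader might infer that re-asking after the teaching is enough to produce a significant result. That cannot be shown. The documents give neither a shift nor an SD, and the table runs from about 7% to over 99%. Only 'can be enough' is supported.

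**The day-2 rating already offers some check.** With #1 vs #2, the planned #2 vs #3 comparison shows whether the rise lasts. This stands as partial mitigation, but persistence is not a comparator.

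**It is a secondary aim in a minimal-risk study,** and the protocol calls the item-level analysis preliminary. That limits the weight of the point, and the movement analysis is unaffected.

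**Conclusion.** The point holds as a limit on interpretation. SE #1 vs #2 can show that ratings changed across the first visit. It cannot show that education caused the change, nor separate teaching from map feedback. The overlap with the map comes from the protocol's own description of the session and would remain even with no response bias.

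The numerical part is conditional. The threshold of 0.37 SD follows from n = 30 and an assumed two-sided 0.05 test with complete data. The 75% to 19% range for a 5-point shift also rests on the assumed SD of 10 to 25 points.

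A reader might also infer that the gain should have to persist to day 2 before Hypothesis 3 counts as supported. The documents do not support that: it would replace their stated immediate hypothesis, and #1 vs #3 is just as uncontrolled.

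This should be corrected, because it changes what the trial may conclude on a secondary aim and costs little.

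**What to change.** In the Data Analysis Plan:

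1. Drop the stated purpose of determining an education effect for #1 vs #2. Describe the contrast as an uncontrolled immediate change after the combined education and map session.
2. State that any cause/effect wording for self-efficacy applies only to the map on/off contrast (#4 to #7), which also settles what the closing paragraph's sentence on self-efficacy covers.
3. Add #1 vs #3 as a supportive description of whether the change lasts to day 2. Say that it is neither a control nor a condition for Hypothesis 3.
4. Report both changes, per item, with 95% CIs.

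**Cost.** Wording and one extra contrast on ratings already collected; no new visits, participants or ratings. The claim for Hypothesis 3 becomes softer. The #1 vs #3 change also mixes modes, since #1 is in person and #3 is by phone, and the report should say so.
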